3.2.3 Efficacy Endpoints

The primary efficacy parameters will be measured between baseline and 26 weeks:

- 1) Change in mitral annular E' velocity will be measured using Tissue Doppler Index (TDI) echocardiography of the left ventricle as a measure of diastolic function and as surrogate measure of left ventricular fibrosis.
- 2) Change in coronary flow reserve (CFR) will be measured using ¹³NH3 myocardial PET scanning as a surrogate measure of microvascular structure and function. CFR will be calculated as the ratio of absolute myocardial blood flow at stress over rest for the entire left ventricle. In the case of flow defects the primary measure of CFR used will be the CFR over flow defect-free portion of the LV.

Preliminary estimates of the impact of ISD/HY on microvascular function can only be evaluated via PET scanning, and will provide a critical metric necessary for understanding the potential of ISD/HY to impact cardiovascular health. Results of PET scanning are thus expected, to provide direct insights into the underlying scientific hypotheses and potential for therapeutic efficacy that serve as a critical complement to the assessment of LV mass and function by echocardiography.

E' has been chosen to be the primary echocardiographic endpoint because the intra-observer coefficient of variation is low¹¹³ and multiple studies demonstrate a high correlation with myocardial fibrosis¹¹⁴⁻¹¹⁶—a primary biologic endpoint of interest. E', for example, parallels the accumulation of myocardial collagen and fibrosis in the senescence prone mouse¹¹⁷, and correlates with endomyocardial fibrosis after human cardiac transplant¹¹⁸ as well as the presence of late gadolinium enhancement¹¹⁹—a highly-validated measure of myocardial scar—across multiple disease states. These and other data demonstrating the strong correlation of TDI with tissue fibrosis across different disease states and

multiple species, strongly establish TDI as a non-invasive marker of myocardial fibrosis well-suited for repeated measure studies. Furthermore, abnormalities in TDI have been strongly linked to mortality in multiple disease states¹²⁰⁻¹²² demonstrating that TDI is a clinically relevant measure. In addition, ESRD-specific studies show that E' is highly correlated with LV mass and other indices of diastolic function, and that changes in E' predict mortality^{39, 123}.

In contrast to other echocardiographic measures, E' (or the ratio of E/E') is minimally affected by intravascular volume status¹²⁴⁻¹²⁶—a critical consideration in ESRD where volume status can vary widely. The adjunctive information on diastolic and systolic function and filling pressures generated by echocardiography provide additional advantages to the use of TDI while the measurement of SR and strain may allow detection of subtle changes in myocardial function due to fibrotic processes¹²⁷. Finally, these measures are known to respond to therapeutic interventions that exert anti-fibrotic effects¹²⁸. Alternative approaches for assessing fibrosis include myocardial biopsy which is considered the gold standard, and cardiac magnetic resonance imaging with gadolinium. However, both of these have risks of serious complications and thus are not suitable for a research study.

CFR has been chosen as the co-primary efficacy endpoint because it is the best available tool for evaluation of microvascular supply and function in the study population. The correlation coefficient for CFR among 4 readers in the proposed study lab was 0.94 indicating excellent reproducibility. In the absence of critical coronary stenosis, hyperemic MBF is determined primarily by capillary density and diameter since capillaries cannot vasodilate in response to adenosine. CFR thus primarily measures microvascular supply, rather than coronary atherosclerosis¹²⁹⁻¹³¹, and it correlates well with human myocardial microvascular histology^{132, 133}. It is strongly associated with mortality¹³⁴, and values are low in CKD and predict a poor prognosis¹³⁵. PET CFR is thus non-invasive, reproducible, well-correlated with myocardial histology, and predictive of outcomes. The gold standard, myocardial biopsy, would be prohibitively risky in this population. Thus, CFR is the best non-invasive endpoint available for assessment of the cardiac microvasculature.

Secondary efficacy endpoints are:

- 1) Change between baseline and 26 weeks in markers of fibrosis and circulating inhibitors of angiogenesis including procollagen type I carboxy terminal peptide (PICP), asymmetric dimethylarginine (ADMA), endostatin (END), angiopoietin II (ANG) and thrombospondin II (TSP)
- 2) Change between baseline and 26 weeks in left ventricular mass index (LVMI). Change between baseline and 26 weeks in ejection fraction. Change between baseline and 26 weeks in myocardial strain and strain rate.
- 3) Change between baseline and 26 weeks in stress and resting myocardial blood flow
- 4) Association between baseline CFR and E'
- 5) Association between change in CFR and change in E'
- 6) Association between baseline ADMA, ANG, END, TSP or PICP and baseline CFR or E'

3.2.4 Feasibility Endpoints

An objective of this study is to assess the feasibility of conducting a large-scale trial powered for clinical outcomes. Feasibility will be assessed based on rates of recruitment, withdrawal, and loss-to-follow-up, reasons for ineligibility, and adherence to the study drug administration schedule.

4 Participant Selection and Withdrawal

4.1 Inclusion Criteria

- a) Maintenance hemodialysis therapy for end-stage renal disease
- b) Age 18-85 years
- c) ≥ 90 days since dialysis initiation
- d) Ability to provide informed consent
- e) All pre-dialysis seated systolic blood pressure measurements must be ≥ 120 mm Hg in the 2 weeks before the screening visit and systolic bp must be ≥ 120 mm Hg on the day of randomization.

4.2 Exclusion Criteria

- a) Serum potassium ≥ 6.5 mEq/L within 2 months prior to screening
- b) Unscheduled dialysis for hyperkalemia within the 3 months prior to screening
- c) Pre-dialysis hypotension defined as pre-dialysis SBP <100 mm Hg (seated measurement) within 4 weeks prior to the screening visit
- d) Recurrent intra-dialytic hypotension defined as either of the following:
 - o systolic blood pressure <80 mm Hg during ≥ 3 dialysis sessions in the 30 days prior to the screening visit, or
 - o treatment for hypotension or symptoms of hypotension during ≥ 3 dialysis sessions in the 30 days prior to the screening visit. For this criterion, hypotension is defined as systolic blood pressure <100 mm Hg.
- e) Mitral valve repair or replacement
- f) Severe mitral valve disease by echocardiography, coronary angiography or cardiac magnetic resonance imaging
- g) Anticipated kidney transplant, change to peritoneal dialysis, or transfer to another dialysis unit within 6 months
- h) Expected survival <6 months
- i) Allergy to study medications (ISD, HY, adenosine or dipyridamole)
- j) Active use of sildenafil, vardenafil or tadalafil
- k) Current severe aortic stenosis or other cause of LV outflow obstruction
- l) Pregnancy, anticipated pregnancy, or breastfeeding, confirmed by serum pregnancy test on the day of PET scan
- m) Incarceration
- n) Participation in another intervention study
- o) Use of monoamine oxidase inhibitors
- p) Contraindication to adenosine including

- 2nd or 3rd degree heart block, sick sinus syndrome or symptomatic bradycardia (without a functioning pacemaker)
- moderate or severe asthma
- chronic obstructive pulmonary disease

q) Active use of any of the study medications unless participant and physician willing to discontinue prior to enrollment.

4.3 Participant Recruitment and Screening

Participants at dialysis units affiliated with investigator and co-investigator practices will be pre-screened for eligibility. In addition to active screening of dialysis unit rosters by study personnel, informational handouts and brochures may be disseminated at affiliated dialysis units in order to allow for interested participants to learn about the study and to contact the study investigator if interested. All study material must be approved by local IRBs before dissemination to potential study participants.

Dialysis unit labs, medical records at the investigator's institution, and treatment or history records at local dialysis units will be reviewed to assess eligibility for enrollment. No study-specific testing is required to confirm eligibility, except a serum pregnancy test (to assess eligibility on the day of PET scan) for women of childbearing potential, and serum potassium if a measurement is not available through clinical measurements within the specified time window. Prior to enrollment, each participant's treating nephrologist will be contacted to assess suitability for enrollment. If a participant is not eligible at the initial screening visit, he/she may be rescreened one additional time, after the appropriate interval has passed.

Once preliminary eligibility is confirmed, informed consent will be obtained by a qualified investigator or study site designee during an in-person visit. This visit may take place either at the local dialysis unit or at the investigator's institution, according to investigator and participant preferences. A randomization/baseline visit will be scheduled within 4 weeks of the screening visit.

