1.4 Dose Rationale and Risks

As noted above (section 1.3), despite the clinical use of the investigational agents individually or in combination in patients with ESRD, ISD/HY combination therapy has not been previously tested in a clinical trial of patients on chronic hemodialysis. Given the absence of dialysis-specific data and the pilot nature of this trial, the starting and target doses were selected on the basis of the doses used in the AHEFT trial⁸⁵ in which combination therapy was associated with significant survival benefits (1.3). Allowances have been made to allow for scheduled dose reductions to the minimum clinical dose of ISD/HY in the event of intolerance. The proposed doses of ISD are equivalent to the doses of isosorbide mono-nitrate that were well tolerated in a 6 month trial of 144 chronic hemodialysis patients¹⁰⁵.

HY is routinely used for clinical purposes in chronic dialysis patients. Although, there is minimal clinical trial data on its use in this setting, HY was well tolerated in a single clinical trial enrolling 18 maintenance dialysis patients¹⁰⁷.

Potential Risks

Both ISD and HY may cause gastrointestinal symptoms, allergic reactions, or decreased blood pressure which could result in light-headedness or symptomatic hypotension, particularly during dialysis. In addition, both ISD and HY (similar to most vasoactive agents) can cause severe hypotension or syncope when given to patients with cardiac outflow obstruction. ISD cannot be given in combination with phosphodiesterase inhibitors used for treatment of erectile dysfunction due to significant hypotensive effects of the combination. Finally, HY can rarely cause a drug associated lupus-like syndrome or peripheral neuropathy when used for prolonged periods. Each of these potential adverse reactions is important, but they should be interpreted within the context of the widespread clinical use of both agents in dialysis patients for many years.

No specific metabolic or hematologic complications of therapy are anticipated. However, to provide an additional margin of safety, participant dialysis laboratory studies will be monitored throughout the trial by coordinating with the outpatient dialysis units and by reviewing labs drawn according to standard clinical schedules.

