In the event of dose-limiting symptoms such as headache, hypotension or gastrointestinal distress, dose increases will be deferred until symptoms have resolved and there has been adjustment to concomitant therapies, diet or dialysis prescription as described in Section 6.7, the dose of study medication or matched placebo may be reduced as applicable. During both the dose escalation phase and the treatment phase, the dose may be reduced to the next lower dose level in the event of adverse events as described in Section 6.7. In order to maintain the blind, all participants will receive blinded medication supplies according to the specified dose within 3 days of the Week 1, Week 2 and Week 4 visits, and within 1 week of the Week 16 week visit, regardless of whether the dose is changed.

Method for Assigning Participants to Treatment Groups

The randomization schedule will be stratified by left ventricular ejection fraction (LVEF) at $\leq 45\%$ vs $> 45\%$ to ensure balance across treatment arms of patients with preserved versus reduced LVEF. A clinical echocardiogram will be used for LVEF determination if available within 6 months. If no echocardiogram is available within the required timeframe then a study cardiologist will perform a limited reading on the study echocardiogram done during the baseline visit. There may be a delay of up to 72 hours between the baseline visit and randomization to allow for the completion of this limited reading.

Randomly permuted blocks of random sizes will be used to control the balance of participants assigned to each treatment regimen within each stratum. This method guarantees that at no time during randomization will the number of participants in any arm be grossly imbalanced, and ensures that the investigator will be unable to predict assignments. All randomization schedules will remain confidential, and known only to authorized members of the central pharmacy.

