6.3 Baseline Visit/Randomization Visit

The baseline visit will be scheduled within 4 weeks of the screening visit. A physical examination will be conducted. Data on medication use, baseline medical conditions, vital signs and edema assessment will be collected. Dialysis prescription, dialysis labs, medications, and vital signs will be updated within 3 days prior to the baseline visit. Serum and plasma will be collected, aliquoted and frozen at -80°C. Additional blood will be drawn for testing of baseline chemistries and blood counts as well as local lab serum pregnancy testing (in pre-menopausal women). Baseline TDI echo and PET scans will be performed. The echo and PET scans are not required to occur on the same day, however, they both should be completed prior to randomization and drug distribution. If LVEF stratification needs to be determined from the baseline echo, then there may be up to a 72-hour delay between the baseline visit and randomization in order to allow for a limited reading of the study TDI echo. A clinical echocardiogram will be used for LVEF determination if available within 6 months of the baseline visit date. Once all the baseline activities have been completed, the patient will be randomized and a 1-week + 3 day supply of study medication will be dispensed. The baseline/randomization visit can be scheduled over two dates within a 10-day window.

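### Undiagnosed outflow obstruction or severe mitral disease could pass screening, because no step before randomisation checks the baseline echocardiogram for it

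*Combined protocol and SAP*

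**What the plan says.** Section 4.2 has three valve or outflow exclusions. Exclusion (e) is surgical history: "Mitral valve repair or replacement". Exclusion (f) is "Severe mitral valve disease by echocardiography, coronary angiography or cardiac magnetic resonance imaging". Exclusion (k) is "Current severe aortic stenosis or other cause of LV outflow obstruction", with no imaging method and no look-back period named.

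Section 4.3 gives the sources for deciding eligibility. Dialysis laboratory results, hospital records and "treatment or history records at local dialysis units will be reviewed to assess eligibility for enrollment", and the treating nephrologist is contacted. On testing it says: "No study-specific testing is required to confirm eligibility, except a serum pregnancy test". The one other exception is a serum potassium when no clinical value falls in the window.

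Section 6.2 confirms eligibility at the screening visit, and the schedule in section 15 marks eligibility at pre-screen and screen only. The baseline echocardiogram and PET scan come later; section 6.3 says "they both should be completed prior to randomization and drug distribution". For stratification, section 5.2 uses a clinical echocardiogram within 6 months. Otherwise: "If no echocardiogram is available within the required timeframe then a study cardiologist will perform a limited reading on the study echocardiogram". Up to 72 hours is allowed for that reading.

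Section 1.4 says that both study drugs "can cause severe hypotension or syncope when given to patients with cardiac outflow obstruction".

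**The concern.** The exclusion that guards against a serious hazard named in the protocol has no defined check in a participant whose records are silent. Records can show that disease is known. They cannot show that a patient without recent imaging is currently free of it. The protocol expects some participants to have no recent clinical echocardiogram, since it arranges a reading for them, but the stated purpose of that reading is LVEF.

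First at stake is safety. A participant with unrecognised outflow obstruction could be allocated to two vasodilators although a study echocardiogram that might have shown the problem had already been acquired.

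Second is the analysis. Section 7.3 keeps everyone randomised in the intention-to-treat population, and the withdrawal list in section 4.4.1 has no entry for an exclusion discovered after randomisation. In a trial of 16, one such participant weighs heavily on the estimates for serious hypotension and for the efficacy measures.

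**Working it through.** No sample size, power or alpha figure is at issue, so the check is mainly a reading of the text in the order a site would follow it.

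1. **Screening (4.2, 4.3, 6.2).** Evidence for (f) and (k) comes from records and the nephrologist. Section 4.3 supplies a fallback test when potassium is missing. It supplies none when imaging is missing.
2. **Baseline visit (6.3).** A physical examination is done and the study echocardiogram is acquired. Neither is linked to (f) or (k).
3. **Reading before randomisation (5.2, 6.3).** The only reading described is conditional on there being no clinical echocardiogram within 6 months, and its stated purpose is the LVEF stratum.
4. **Full reading (6.9.1).** The listed measurements are E', mitral inflow E and A, LV mass index, LVEF, strain and strain rate, analysed blinded and off-line. No valve grading or outflow measurement is named, and no deadline before randomisation is set.
5. **Release to randomise (5.2).** Eligibility data must be entered and the study team must agree that all criteria are met. The text does not say what evidence supports that agreement for (f) and (k).

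So a participant with undiagnosed or outdated disease and no recent imaging can pass every step as written.

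**Exposure.** Allocation is 1:1 (3.1), so such a participant has a 1/2 = 50% chance of active drug. One participant is 1/8 = 12.5% of an arm.

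**Illustration only.** The documents give no prevalence of undetected disease among those who would be randomised. Let p be an assumed value. The chance of at least one affected participant among n is 1 − (1 − p)^n. With n = 8 this formula reproduces all six rows of Table 2 in section 7.1; for example, p = 0.05 gives 0.3366 against 0.34, and p = 0.10 gives 0.5695 against 0.57.

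| Assumed p | At least one of 16 randomised | At least one of 8 on active drug |
|---|---|---|
| 0.01 | 0.149 | 0.077 |
| 0.02 | 0.276 | 0.149 |
| 0.05 | 0.560 | 0.337 |
| 0.10 | 0.815 | 0.570 |

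The table shows only how the result depends on p. It does not estimate the risk in this trial.

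**The case against.** The strongest reply is that (f) and (k) are exclusions of documented disease. On that reading sections 4.2 and 4.3 do not conflict: records are searched, the nephrologist is asked, the patient is examined, and the team must agree on every criterion before randomisation. Nothing forbids the cardiologist from acting on a severe incidental finding. A manual of procedures (9.1.1), which is not among the documents, may say more. The per-protocol population in section 7.3 also requires appropriate randomisation, so a supplementary analysis without a wrongly entered participant is available.

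Most of this stands for known disease. It does not supply evidence about undiagnosed or outdated disease, and the protocol itself does not ask for any.

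Four stronger readings are tempting, and the documents do not support them:

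- A reader might infer that the exclusions can be met only with an echocardiogram. Exclusion (f) also accepts angiography or MRI, (k) names no method, and (e) is history.
- A reader might extend the warning in section 1.4 to mitral disease. The text ties it to outflow obstruction only. That severe mitral disease would disturb E' is an inference from where E' is measured; the protocol does not say so.
- A reader might count everyone without a recent clinical echocardiogram as at risk. If that share were assumed to be 25% to 75%, it would be 16 × 0.25 = 4 to 16 × 0.75 = 12 participants. The share is not in the documents, some of these people may have other or older imaging, and lacking a recent scan is not having the disease. The 6-month limit was set for LVEF, not for valve status.
- A reader might assume that an affected participant would receive the vasodilators. Half would be expected to receive placebo.

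**Conclusion.** The gap is real but narrow. As written, the plan relies on records for exclusions (f) and (k) and gives no rule for a participant whose records contain no relevant imaging, although a study echocardiogram is acquired before randomisation in everyone. It matters chiefly for (k), because section 1.4 names severe hypotension or syncope in that setting. The same gap applies to (f), without that named hazard.

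Its size cannot be computed from the documents. It depends on how many participants lack recent imaging and on how common undetected severe disease is among them, and neither is given. No sample size or power figure changes.

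The conclusion rests on the protocol text alone; a manual of procedures could already close the gap in practice. This is a specification point worth correcting because the correction is cheap. It is not an internal contradiction that must be resolved.

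**What to change.** Reconcile sections 4.2, 4.3, 5.2 and 6.3 so that they state what imaging evidence satisfies (k) and (f) and how recent it must be. The sponsor should set that period on its merits and not carry over the LVEF window by default. In section 4.3, add the check for (k) and (f) to the listed exceptions, next to the potassium fallback.

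Where no qualifying evidence is on record, have the study cardiologist's limited reading of the baseline echocardiogram also report whether (k) or (f) is present, within the existing 72-hour allowance. Make the answer a required eligibility entry before randomisation, and add an eligibility mark at the baseline visit in section 15.

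The cost is protocol wording, one form field and a slightly longer reading. Because section 6.9.1 names no valve grading or outflow measurement, a few standard views may have to be added to the acquisition. An occasional participant would fail screening after baseline imaging has already been done.

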4.4 Early Withdrawal of Participants

4.4.1 When and How to Withdraw Participants

Early withdrawals will be discouraged and participants who are not willing to continue the intervention will be encouraged to remain in the study and continue study evaluations. However, participants may be withdrawn from the study under the following circumstances that have the potential to compromise patient autonomy or safety:

- a) Pregnancy
- b) Withdrawal of consent
- c) Allergy to or documented intolerance of study medications (e.g. recurrent hypotension on the lowest dose of study medications)
- d) Non-compliance with dialysis schedule compromising ability to follow serum potassium on a monthly basis
- e) Organ transplantation
- f) Change to a different dialysis modality

- g) Initiation of sildenafil, vardenafil or tadalafil therapy
- h) Transfer to non-participating dialysis unit

